A double-blind, placebo-controlled, randomized study examining the effects of nebivolol compared to atenolol on endothelial function and cardiovascular risk in patients with early vascular disease.

EVIDENCE: Early Vascular Impairment-Determine Efficacy of Nebivolol, Comparator Examination

Principal Investigator: [name]

Co-Investigators: [name], PhD
[name]
[name]

Version Date: January 14, 2014

University of Minnesota Medical School, Cardiology Division

PI Contact Information:

Mail: [name]
[name]

[contact]

[contact]

e-mail: [contact]

Table of Contents

STUDY SCHEMA	3
1. INTRODUCTION AND SCIENTIFIC RATIONALE	4
2. STUDY DESIGN	4
3. METHODOLOGY	4
4. OBJECTIVES	5
5. SELECTION OF PATIENTS	6
6. RANDOMIZATION PROCEDURES	7
7. TREATMENT PLAN	8
8. STUDY PARAMETERS	10
9. STUDY ENDPOINTS	12
10. ADVERSE EVENT REPORTING	13
11. DATA AND SAFETY MONITORING PLAN	16
12. STATISTICAL CONSIDERATIONS	16
13. ADMINISTRATIVE REQUIREMENTS	17
14. REFERENCES	18

STUDY SCHEMA

[figure not shown]
Study Population:

- Males and females between 18 and 80 years of age with early vascular disease
- Borderline blood pressure (120-145/80-90 mm Hg)
- Borderline or abnormal small artery elasticity (C_2) as measured by pulse contour analysis
- Treatment-naïve for all blood pressure medications including diuretics for at least 30 days prior to baseline visit
- No known history of cardiovascular disease

Accrual Goals:

75 patients enrolled.

Treatment Plan:

Schedule of Assessments:

- **Blood pressure at rest at 0, 1, 3, 6 and 9 months**
- **Small artery elasticity (C_2) and flow-mediated dilation at 0, 1, 3 and 9 months**
- **Rasmussen Disease Score assessments** (large artery elasticity, carotid intima-medial thickness, electrocardiogram (ECG), treadmill exercise test and left ventricle ultrasound) **at 0, 3 and 9 months**
- **Cardiac Health Biomarkers** (Total cholesterol, LDL, HDL, triglycerides, glucose, hsCRP, microalbuminuria and NT-proBNP) **at 0, 3 and 9 months**

1. INTRODUCTION AND SCIENTIFIC RATIONALE

β -blockers have been widely used for the treatment and prevention of cardiovascular disease for more than three decades. In recent years, β -blocker usage has declined as studies have shown that traditional β -blockers have little effect on peripheral resistance, which is increased in individuals with endothelial (vascular) dysfunction [1-3]. Recently, nebivolol, a third generation β -blocker, was approved for use in the United States.

Nebivolol is a highly selective β_1 -blocker with vasodilating effects that reduce peripheral resistance. Vasodilation is mediated by nebivolol's action at multiple points in the nitric oxide (NO) pathway [4]. The NO-mediated vasodilation of nebivolol is novel among β -blockers and is particularly promising as impaired vascular function in patients with cardiovascular disease may be due in part to decreased endothelial NO bioavailability [5]. Studies in patients with hypertension and/or coronary artery disease have shown that nebivolol improves endothelial function while non-vasodilating β -blockers do not [6, 7]. The efficacy of nebivolol on endothelial function in low to moderate risk populations has not been well documented.

We propose to study nebivolol in subjects with early vascular disease, using atenolol as an active comparator, as both drugs are selective β_1 -blockers with no α -blocking capabilities. These drugs differ in the fact that atenolol does not have vasodilating properties [6]. We hypothesize that both drugs will likely lower blood pressure through β_1 -receptor blocking but only nebivolol will improve impaired endothelial function, presumably through NO-mediated vasodilation. A placebo arm will also be employed to further differentiate these two treatment strategies.

2. STUDY DESIGN

This is a randomized, double-blind, placebo-controlled study comparing the efficacy of nebivolol and atenolol at improving small artery elasticity and reducing cardiovascular disease risk in subjects with early vascular disease. Approximately 75 subjects with borderline/elevated blood pressures and impaired endothelial function, as measured by arterial elasticity scores, will be recruited and assigned to treatment groups using a block randomization scheme. Patients will be randomly allocated to nebivolol, atenolol or placebo, and then followed for 9 months.

3. METHODOLOGY

The Rasmussen Disease Score (RDS) test panel is the chosen methodology for this study. The 10 parameters of the RDS were selected because of their ability

to quantify early structural and functional abnormalities in the vasculature and left ventricle which appear long before cardiovascular disease is present [8].

The RDS tests include: large and small artery elasticity (measured by pulse contour analysis), resting blood pressure, mild treadmill exercise test, carotid IMT, left ventricle mass, ECG, retinal vasculature evaluation, as well as quantification of serum NT-proBNP, and microalbuminuria. Please see Section 8 for a more detailed description of these parameters. Quantitative results from these tests are converted into categorical classifications based on values stratified by age and gender when appropriate. The categorical data is scored as follows: normal = 0 points, borderline = 1 point, abnormal = 2 points. Point values from all parameters are summed to create the RDS, with values ranging from 0-20. Scores of 0-2 are classified as normal, 3-5 as early disease, and 6+ as advanced disease. Previous research has shown that the RDS is a powerful predictor of future cardiovascular events [9].

The small artery elasticity (C_2) parameter is of particular interest as it is responsive to changes in NO levels [10] and is an effective and reliable predictor of future hypertension [11] and other cardiovascular events [12]. Changes in C_2 will serve as the primary outcome of this study. Similar studies using anti-hypertensive or lipid-lowering interventions have found significant improvements in C_2 values [13, 14].

Brachial artery flow-mediated dilation (FMD) measurements will also be measured as an index of endothelial function [15], although this method appears to be less sensitive to functional changes related to NO bioavailability than C_2 [10]. Utilizing both FMD and C_2 will allow comparison with previous studies and take advantage of a large sample size to further examine the relative sensitivity of each method for reliably measuring endothelial dysfunction.

The duration of intervention for this study is 9 months which is the minimum time to adequately detect improvement in left ventricle (LV) mass values. LV mass measurements are a critical component of a comprehensive assessment of cardiovascular health and have improved within this temporal window as a result of anti-hypertensive intervention [14, 16].

4. OBJECTIVES

4.1. Primary Objective

This study will compare the effects of nebivolol against atenolol and placebo on endothelial function. Endothelial function will be measured by pulse contour analysis of the small arteries and scored in terms of arterial elasticity over a 9 month study period.

4.2. Secondary Objectives

- 4.2.1 Evaluate the effects of nebivolol as compared to atenolol and placebo on cardiovascular health in subjects with early vascular disease as measured by change in Rasmussen Disease Score (RDS) over a 9 month study period.
- 4.2.2 Evaluate changes in each RDS component over the 9 month study period in all treatment groups.
- 4.2.3 Evaluate the changes in risk factor and biomarker measurements from baseline to 3 and 9 month time points in all treatment groups.
- 4.2.4 Compare the sensitivity of pulse contour analysis and flow-mediated dilation methodologies for measuring functional changes in the endothelium and quantifying endothelial dysfunction.

5. SELECTION OF PATIENTS

Study entry is open to patients regardless of gender or ethnic background. Patients will be recruited from the Rasmussen Center for Cardiovascular Disease Prevention at the University of Minnesota, Fairview Clinics, and through advertisements or flyers posted at the University of Minnesota and surrounding communities.

5.1 Inclusion criteria

- Males and females 18-80 years of age
- Borderline blood pressure (120-145/80-90 mm Hg)
- Borderline or abnormal small artery elasticity (C₂) as measured by pulse contour analysis
- Treatment-naïve for all blood pressure medications including diuretics for at least 30 days prior to baseline visit
- Able to walk on a treadmill for 3 minutes
- Female patients with reproductive potential must use an approved contraceptive method if appropriate (for example, intrauterine device [IUD], birth control pills, or barrier device) during and for 1 month after the last dose of study drug.
- Voluntary written informed consent before performance of any study-related procedure not part of normal medical care, with the understanding that consent may be withdrawn by the subject at any time without prejudice to future medical care.

5.2 Exclusion criteria

- History of intolerance to β -blockers or clear contraindications to their use
- Current pharmaceutical treatment of blood pressure
- Known history of cardiovascular disease (myocardial infarction, coronary artery bypass graft, unstable angina, uncontrolled arrhythmias, stroke, etc.)
- Known history of diabetes
- Known history of hepatic, renal, or gastrointestinal disorder
- Known history of any illness that may cause additional risk (as determined by study investigator)
- Pregnant or lactating women. When used during pregnancy, β -blockers may cause fetal harm.
- Participation in a concomitant clinical trial

5.3 Concomitant Therapy

Concomitant medications may include aspirin, birth control pills, lipid lowering agents, anti-platelet medications, psychotropic agents, vitamins or warfarin. The following medications may not be taken during the trial:

- Anti-hypertensive medications
- Vasoactive medications
- Cardiac medications (including β -blockers)

Since statins are known to positively influence arterial elasticity, it is necessary to control their use. Any study subject taking statins must be on a stable dose for 8 weeks prior to the baseline visit. This time window was chosen based on a previous study examining the effects of statin combined with an anti-hypertensive medication on C_2 [13]. There was not a significant improvement in C_2 between the 8 week and 28 week time points in the groups receiving a statin.

Subjects will be instructed to maintain their established statin regimen throughout the duration of the study.

6. RANDOMIZATION PROCEDURES

Randomization will occur after informed consent has been obtained and after eligibility is confirmed by measuring blood pressure and small artery elasticity. Two 1:1:1 randomization lists (one for subjects taking a statin and one for subjects without statin therapy) generated by variable block randomization will be used to assign each subject to a study arm at the time of enrollment. This method will allow stratification of statin therapy.

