9. STUDY ENDPOINTS

9.1 Primary Endpoint

Change in small artery elasticity (a marker for endothelial function) from baseline to 9 months after intervention initiation.

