12.1 Statistical Methodology

The primary analysis of the study is descriptive, to obtain a point estimate and 95% confidence interval of the difference in small artery elasticity (C_2) between nebivolol and atenolol treatment arms and nebivolol and placebo at the end of the observation period (9 months). Point estimates and 95% confidence intervals for the improvement in C_2 within each treatment will also be presented.

Secondary analysis estimating difference in Rasmussen Disease Score (RDS) improvement between the nebivolol and atenolol treatment groups along with nebivolol and placebo groups at the end of the observation period (9 months) will also be completed.

Other secondary analyses include estimates of the associations among changes in RDS as well as risk factor and biomarker measurements from baseline to the 3, and 9 month time points in the two positive comparator groups.

Unpaired t-tests will be used to compare the means of C_2 (small artery elasticity) as well as all RDS test component and biomarker values for each subject group at each time point. Paired t-tests will be used to compare baseline values and values from subsequent time points within one group. A P-value of < 0.05 will be considered statistically significant.

Comparison of sensitivity and variability for C₂ and flow-mediated dilation (FMD) methodologies used in quantifying endothelial function of each group over the 9 month study period will also be included in the secondary analyses. Data will be analyzed within and between test groups with a significance level of $P \leq 0.05$.

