12.2 Design and Sample Size Justifications

A sample size of 25 subjects per arm will be adequate to detect a difference in small artery elasticity of 3.3 units (ml/mm Hg x 100) between positive comparators when power = 0.9 and $\alpha = 0.05$. This is assuming a standard deviation of ± 3.57 units. This assumption is made based on a previous clinical trial measuring small artery elasticity in patients undergoing anti-hypertensive therapy [14].

Subjects in the previous study were not selected on the basis of C₂ as they are in EVIDENCE. Therefore, it is reasonable to assume that our actual standard deviation will be much smaller than our estimate giving us a conservative population sample of 75. Assuming a smaller deviation of 3.0 (instead of 3.57) we would still have an adequate sample with a dropout rate of 7.6%. If rates of attrition exceed 7.6%, subjects will be replaced

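### Randomisation is stratified by statin use but the between-arm analysis ignores the stratum, so if statin users and non-users differ in C2 the test is conservative and the interval wider than needed

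*Combined protocol and SAP*

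**What the plan says.** **Allocation.** Section 6 assigns patients from "Two 1:1:1 randomization lists (one for subjects taking a statin and one for subjects without statin therapy) generated by variable block randomization" and gives the purpose: "This method will allow stratification of statin therapy".

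**Reason for the factor.** Section 5.3: "Since statins are known to positively influence arterial elasticity, it is necessary to control their use". Statin users must be on a stable dose for 8 weeks before baseline and are told to keep to their regimen. The section supports the 8-week window with an earlier study: "There was not a significant improvement in C_2 between the 8 week and 28 week time points in the groups receiving a statin".

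**Endpoint.** Section 9.1: "Change in small artery elasticity (a marker for endothelial function) from baseline to 9 months after intervention initiation".

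**Analysis.** Section 12.1 calls the primary analysis descriptive. Its aim is "to obtain a point estimate and 95% confidence interval of the difference in small artery elasticity (C_2) between nebivolol and atenolol treatment arms", and likewise for nebivolol against placebo, at 9 months. No method is named for that interval. The only between-arm method in the section is: "Unpaired t-tests will be used to compare the means of C_2", applied at each time point. Paired t-tests are also named, but only within an arm. No section contains a stratum term, a stratified test or a covariate-adjusted model.

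**Size.** Section 12.2 plans 25 per arm to detect 3.3 units with power 0.9 and alpha 0.05. "This is assuming a standard deviation of ± 3.57 units".

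**The concern.** The protocol treats statin use as important enough to C2 to constrain the allocation, then leaves it out of the analysis. That is a mismatch between design and analysis. Blocking within strata makes the statin mix nearly equal across arms, so a C2 difference between users and non-users contributes almost nothing to the true sampling variance of the arm contrast. An unpaired t-test estimates its error variance from all patients in an arm regardless of stratum, so it includes that difference. If the strata differ, the standard error is overstated, the test rejects less often than its nominal level, and the interval covers more than 95%.

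The main product of this trial is a set of 95% intervals from about 25 patients per arm. At stake is precision that the randomisation has already provided and the analysis would not use. Validity is not at stake.

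**Working it through.** **Inputs from the protocol.** 75 patients, 1:1:1, 25 per arm; SD 3.57; difference 3.3 units; alpha 0.05; power 0.9 (Section 12.2). Two strata by statin use, variable blocks (Section 6).

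**Assumptions, because the documents give no figures.** Statin share p = 10%, 30% or 50%. Difference in mean analysed C2 outcome between strata D = 0, 1, 2 or 3.57 units (the last is one SD). Block sizes 3 and 6. Same treatment effect and same SD in both strata; no missing data. The unpaired t-test is taken to supply the primary interval, which is an inference because Section 12.1 does not name the method.

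**Step 1: reproduce the plan.** n per arm = 2 × (1.960 + 1.282)² × 3.57² / 3.3² = 24.6, rounded up to 25. This matches Section 12.2 with a two-sided alpha (one-sided would give 21). Power at 25 per arm is 0.905 by the normal approximation and 0.893 by the noncentral t. The sample size is not in error.

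**Step 2: split the variance.** Total variance is 3.57² = 12.745. The between-stratum part is p(1−p)D², and the within-stratum SD is √(12.745 − p(1−p)D²). Holding the total at 3.57 keeps the comparison tied to the protocol's own figure.

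**Step 3: half-widths at p = 30%.** Unadjusted: 2.0106 × 3.57 × √(2/25) = 2.030 (48 df). Adjusted: 2.0117 × within-stratum SD × √(2/25) (47 df for the two-arm comparison). Approximate true type I error of the t-test: 2 × [1 − Φ(1.96 × 3.57 / within-stratum SD)].

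| D (units) | p(1−p)D² | Within-stratum SD | Unadjusted half-width | Adjusted half-width | Unadjusted wider by | Type I error, unadjusted |
|---|---|---|---|---|---|---|
| 0 | 0 | 3.570 | 2.030 | 2.031 | −0.1% | 5.0% |
| 1 | 0.21 | 3.541 | 2.030 | 2.015 | 0.8% | 4.8% |
| 2 | 0.84 | 3.450 | 2.030 | 1.963 | 3.4% | 4.3% |
| 3.57 | 2.68 | 3.173 | 2.030 | 1.806 | 12.4% | 2.7% |

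**Step 4: check by simulation.** 20,000 trials per setting, with stratified permuted blocks, comparing the pooled t-test with a linear model containing arm and stratum. The Monte Carlo standard error of the type I error is √(0.05 × 0.95 / 20,000), about 0.15 percentage points. At p = 30%:

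- D = 0 to 1: unadjusted interval 0–1% wider; type I error about 5%.
- D = 2: half-width 2.02 against 1.95 (3.5% wider); type I error 4.2% against 5.0% adjusted; unadjusted coverage 95.8%.
- D = 3.57: half-width 2.03 against 1.80 (13% wider); type I error 2.7% against 5.0%; unadjusted coverage 97.3%.

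**Step 5: other statin shares.** At 10%, the unadjusted interval is 1.3% wider at D = 2 and 4.7% at D = 3.57. At 50%, it is 4.2% and 16% wider.

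**Step 6: power and bias.** For a true difference of 3.3 units at p = 30%, unadjusted power stays at 0.89–0.92. Adjusted power is 0.89, 0.90, 0.91 and 0.95 at D = 0, 1, 2 and 3.57. Mean bias of the unadjusted estimate is under 0.02 units in every setting.

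**The case against.** The strongest reply is that the loss may not arise for the declared endpoint. Section 9.1 defines a change from baseline, and a stable difference between users and non-users cancels in a change score. Statin doses are held stable, and the study cited in Section 5.3 showed no significant further C2 improvement between weeks 8 and 28. This stands: for change, D may be near zero. But Section 12.1 describes the difference in C2 at 9 months and tests means at each time point. Those are levels, where a stable difference would remain.

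Second, the larger losses need a large D. The 3.57-unit row exceeds the 3.3-unit treatment difference that the trial is sized for, in patients who under Section 5.1 are all selected for borderline or abnormal C2. Even the sign of D is unknown, since statin users may start at higher risk. This also stands, and is why the result is given as a range. A difference below about 1 unit costs almost nothing.

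Third, planned power is kept, the estimate is unbiased, and the analysis is descriptive in a Phase II trial. That is true, but an analysis whose product is an interval has most reason to care about interval width.

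Fourth, adjusting for baseline C2 would probably absorb much of a stable statin difference, and Section 5.3 ties statins only to arterial elasticity, not to the Rasmussen Disease Score (RDS). Baseline adjustment is compatible with a stratum term. The case for reflecting the stratification in the analysis applies to every outcome, although no size was calculated for RDS.

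These points limit the magnitude. None supplies a reason to leave the stratum out.

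**Conclusion.** The concern holds, as a conditional matter of efficiency. The stratification factor is absent from the only between-arm method named. If statin users and non-users differ in the analysed C2 outcome, the unpaired t-test is conservative and its interval too wide. At a 30% statin share the excess width runs from nothing at no difference, through about 3.5% at 2 units, to about 13% at one SD; across shares of 10–50% the one-SD figure runs from 4.7% to 16%. False positives are not inflated, the estimate is unbiased, balance by statin use is still achieved and planned power is kept.

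The size depends on an assumed statin share and stratum difference, on total SD 3.57, and on the t-test supplying the primary interval. It bears mainly on C2 levels and may vanish for change scores. The change is worth making because it costs almost nothing even when the strata do not differ.

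**What to change.** In Section 12.1, state that the nebivolol–atenolol and nebivolol–placebo differences in C2, with their 95% confidence intervals, are estimated from a linear model with treatment arm and the statin stratum used at randomisation. Use the same model for RDS and its quantitative components. This also names the interval method that Section 12.1 leaves open. The same sentence should say whether the outcome is the 9-month level or the change from baseline; baseline C2 can be added as a covariate at that point.

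The cost is one sentence and one degree of freedom for the stratum term. The sample size is unchanged. With no stratum difference, the half-width is 2.02 with or without the term in simulation (2.030 against 2.031 analytically).

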7. TREATMENT PLAN

7.1 Administration Schedule

Depending on assigned treatment group, subjects will take nebivolol, atenolol, or placebo. Matching medications necessary for maintaining the double-blind nature of the study will be provided by Forest, Inc.

Nebivolol 5 mg will be taken once daily with or without food by mouth for the first month. At the 1 month visit, nebivolol will be increased to 10 mg per day and will be taken for up to 8 months.

Atenolol 25 mg will be taken once daily with or without food by mouth for the first month. At the 1 month visit, atenolol will be increased to 50 mg per day and will be taken for up to 8 months.

Placebo will be taken in the same manner as nebivolol and atenolol treatment groups.

Patients will return to clinic at 1, 3, 6 and 9 months (+/- 1 week) for evaluation and a compliance check.

Patients will be instructed to return all study drug bottles and any remaining tablets to each appointment where subject compliance will be assessed by performing tablet counts.

Patients who demonstrate non-compliance during the study will be counseled regarding proper administration of study medication. In cases of continued and/or extreme non-compliance, study participation may be discontinued.

